
Aims 2 and 3 of the RCT will be completed simultaneously. The total targeted population for Aims 2 and 3 of the RCT are 240 enrolled patient/family dyads and a maximum of 60 randomized clinicians. To be considered "enrolled" for this study, a patient/family dyad must meet all eligibility criteria and receive a NEST score of > 15.

For aims 2 and 3, the study team will conduct a randomized clustered clinical trial. Randomization occurs at the ICU clinician level versus that of the patient/family level. Clinicians are identified as eligible if they are the current attending on service for the particular ICU. Clinicians are randomized to one of the two arms based on the following:

- 1. Gender (male/female)
- 2. Clinical Experience (<10 years vs > 10 years)
- 3. Discipline (medical vs. surgical)

Consented, enrolled clinicians are expected to complete the following survey(s):

• Baseline Demographics Survey (on the day of consent)

For those clinicians who are randomized to intervention, they will be required to complete the following:

- Review patient/family needs score and survey results within ICUconnect (at the completion of T1 by patient/family dyad)
- Schedule and conduct a family meeting (after T1 completion but before T2 completion)
- Review patient/family needs score and survey results within ICUconnect (at the completion of T2 by patient/family dyad)
- Complete the Clinician Survey via ICUconnect (after Family Meeting and completion of T1 and T2 by patient/family dyad).

Patient/family dyads will be identified at the time of ICU admission and approached for consent based on meeting study inclusion/exclusion criteria (see Selection of Subjects). Each patient/family member, if enrolled into the RCT will be asked to complete an ICUconnect profile and survey (T1). This survey is to be completed within 24 hours of consent to the study. Given that this study's intent is to address unmet needs, eligible participants must receive a NEST score of > 15 (see Study Eligibility Workflow).

- If a participant receives a NEST score of < 15 and they are assigned to a randomized intervention clinician, the participant is considered a screen failure.
- If a participant receives a NEST score of < 15 and is assigned to a randomized control clinician, the
 participant is considered a screen failure for the RCT but is allowed to continue participation within
 the ancillary study.

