General considerations: The primary analyses will be conducted on an intention-to-treat basis; clinicians and patients will be analyzed in the group to which they were randomized, regardless of clinician intervention adherence, using all available data. The main conclusions drawn from this trial will be based on the pre-specified hypotheses outlined below and will be tested with two-sided p-values at the standard 0.05 level. For all study outcomes, we will interpret differences between groups over time with reference to prior literature regarding clinically meaningful changes. Results from exploratory analyses will be interpreted with appropriate consideration for their exploratory nature. Statistical analyses will be performed using the latest release SAS for Windows (Cary, NC) and R/Rstudio.

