
Power and sample size considerations. For Aim 1, to reach a target of 'excellent' usability (mean SUS score >85), we expect 1-2 iterative revision cycles of 8-15 family members and 8-10 clinicians—a sample similar in size to that needed to reach thematic saturation in qualitative analysis (e.g., the 30 patient-level cases (total n=90) we expect will allow us to recognize theme saturation in Aim 4). The effect of interest for Aims 2 and 3 is essentially the T1 - T2 difference between the intervention and usual care groups. Aim 2 focuses on the overall difference and the difference within Black and White patients separately, while Aim 3 focuses on the difference within Black families compared to White families. Therefore, we base our sample size calculations on the mean difference score using tests for two means in a cluster randomized design. The sample size requirements are greatest for Aim 3; as discussed by Leon and Heo (2009), the needed sample size for the family race by intervention group interaction is 4 times that needed for the overall test. Based on preliminary studies, the standard deviation of the change in NEST score is estimated as 12 units and a reasonable range of intraclass correlation coefficients is 0.01 to 0.1. For all calculations, the type I error is 5% and power is 80%. With a sample size of 160 families (4 per each of 40 physicians. 20 per treatment arm), we will be able to detect differences of 4.0 to 5.0 NEST units for Hypothesis 2a in the overall test, 5.4 to 6.1 for Black or White patients separately, and 7.6 to 8.0 units for Hypothesis 3a. For Aim 4, we expect that up to 25 cases comprised of family members will be sufficient to reach informational redundancy—the point at which no new themes emerge.

Ancillary study: Needs and triggers: improving intensive care unit-based palliative care deliveryStatistical methods:

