NCT03506438

Full Title: Addressing Palliative Care Needs Among Intensive Care Unit Family Members

Document Date: 04/28/2021

Statistical Analysis Plan (Pro00090202)

Statistical Analysis Plan

The goal of the primary hypothesis was to determine the efficacy of the ICUconnect intervention versus usual care on reduction in unmet needs from T1 to T2. Unmet needs were assessed at T1, T2, and T3 with the total NEST score, a continuous, normally distributed measure. Because each family member was surveyed at multiple time points and the same ICU physician saw several patients, outcome variable measurements were not be independent. Therefore hierarchical linear models fit via PROC MIXED in SAS 9.4 (Cary, NC) were used as the primary analytic strategy they appropriately accounted for the multiple types of correlation inherent in our study design. The other continuous, longitudinal outcomes included: PHQ-9, GAD-7, PTSS, and QOC; hierarchical linear models were also used to estimate the treatment effect over time for these outcomes. The binary outcomes of goal concordant care and IPC (dichotomized due to ceiling effects) were analyzed via generalized linear models with a logit link and fit with generalized estimating equations (PROC GENMOD in SAS, 9.4). Finally, treatment group differences in hospital and ICU length of stay were examined with a Wilcoxon test.

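### The length-of-stay comparison uses a Wilcoxon test that ignores clustering by the randomised clinician, so its nominal 5% level is probably somewhat exceeded

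*SAP*

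**What the plan says.** The protocol (Design & Procedures, Aims 2 and 3) states: "Randomization occurs at the ICU clinician level versus that of the patient/family level". The SAP, a single paragraph, gives the consequence: because "the same ICU physician saw several patients, outcome variable measurements were not be independent".

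It then chooses methods that can carry this dependence for most outcomes. For the continuous longitudinal outcomes, "hierarchical linear models were also used to estimate the treatment effect over time for these outcomes". The binary outcomes were "analyzed via generalized linear models with a logit link and fit with generalized estimating equations". The closing sentence is different: "treatment group differences in hospital and ICU length of stay were examined with a Wilcoxon test". It names no cluster, clinician-level summary or stratum. The protocol contains no other analysis of length of stay.

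**The concern.** The null variance of the two-sample Wilcoxon statistic is derived for independent observations. Here all families of one clinician share an arm, so variation between clinicians enters the arm contrast in full. The ordinary test counts families as the independent units and leaves that variation out.

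Stay could well cluster by clinician. Clinicians are enrolled as the attending of a particular ICU, and the study ICUs are medical, surgical, cardiac, cardiothoracic and neurological, plus those at a second hospital. At stake is whether a chance difference between a few attendings is reported as a shorter or longer stay due to the intervention. The plan does not argue that clustering is negligible for stay; its stated premise is the opposite.

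**Working it through.** **Inputs**

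- Level: the main hypotheses "will be tested with two-sided p-values at the standard 0.05 level" (protocol, Aim 2 general considerations). I assume the same level for stay.
- ICC: 0.01 to 0.1, from the power section, where it accompanies an SD of 12 for NEST change. This concerns NEST; no value is given for stay, so the range is borrowed.
- Caseload: 160 families as 4 for each of 40 physicians (power section); 240 dyads over 30 to 60 clinicians (Subject Recruitment and Compensation), so a mean of 240/60 = 4 to 240/30 = 8.

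**The plan's own figure.** The documents state no error rate specific to the stay comparison. The nearest figure is the detectable NEST difference for Hypothesis 2a, given as 4.0 to 5.0. The usual formula, (1.96 + 0.84) × 12 × √(2 × DE/80), gives 5.4 with DE = 1.03 and 6.1 with DE = 1.30, so that figure does not reproduce for 160 families. That is a separate matter, and nothing below depends on it.

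**True size of the unadjusted test.** With m families per clinician, the design effect is DE = 1 + (m − 1) × ICC. The size of a nominal two-sided 5% test that ignores it is 2 × [1 − Φ(1.96/√DE)].

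| Layout | m | DE (ICC 0.01; 0.1) | Size, ICC 0.01 | Size, ICC 0.1 |
|---|---|---|---|---|
| 160 over 40, or 240 over 60 | 4 | 1.03; 1.30 | 5.3% | 8.6% |
| 240 over 40 | 6 | 1.05; 1.50 | 5.6% | 11.0% |
| 240 over 30 | 8 | 1.07; 1.70 | 5.8% | 13.3% |

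For the last cell, 1.96/√1.70 = 1.503, and 2 × [1 − Φ(1.503)] = 13.3%.

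Simulated null trials with a normal clinician effect agree. At ICC 0.1 the Wilcoxon test rejected in 8.1% to 8.4% of trials at m = 4, 10.7% at m = 6 and 12.5% to 13.0% at m = 8. At ICC 0.01 it rejected in about 5% to 6% in every layout.

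**Unequal caseloads.** With 240 families over 30 clinicians, ICC 0.1 and a coefficient of variation of caseload of about 0.5 (assumed), the simulated size is about 15%.

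**Discipline.** The table ignores that randomisation is stratified by medical or surgical discipline. Null trials with clinicians randomised within discipline and a total ICC of 0.1 gave the following (8,000 trials each; the share due to discipline is assumed):

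| Share of between-clinician variance due to discipline | 40 × 4 | 40 × 6 | 30 × 8 |
|---|---|---|---|
| None | 9.0% | 11.2% | 13.2% |
| Half | 6.2% | 7.2% | 8.9% |
| Three quarters | 5.0% | 5.5% | 7.4% |

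A repeat run agreed to within 1 percentage point. If a discipline effect of 0.6 SD is instead added on top of a residual ICC of 0.1, the offset is smaller: 8.2% falls to 7.3%, 10.8% to 9.3% and 13.1% to 12.4%.

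**After correction.** A t-test on clinician mean ranks, with degrees of freedom equal to clinicians minus 2, had a simulated size of 4.7% to 5.1% in each setting tried: 40 × 4, 60 × 4 and 30 × 8 at both ICCs, and the unequal caseloads at ICC 0.1.

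**The case against.** The strongest reply has three parts.

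First, stay is peripheral. Aims 2 and 3 concern unmet needs and quality of patient-centred care. The protocol rests its main conclusions on the pre-specified hypotheses and promises caution with exploratory results. This stands, and it limits the severity.

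Second, the ICC is borrowed. The post-consent exclusions require the randomised physician to stay on service for only about 2 calendar days after T1, so much of a hospital stay may fall under other attendings. Clustering by index attending could be weak, and at ICC 0.01 the inflation is trivial. This stands against any firm figure. It does not rescue the test, because the plan neither claims nor shows that the correlation is zero.

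Third, stratified randomisation works against the inflation. A reader might count the lack of stratification in the test as a further source of false positives, since stay may differ between medical and surgical ICUs. The direction is the reverse: balancing the arms on a prognostic factor and then ignoring it makes a test conservative. The second table shows that this offsets part of the inflation. Stratifying would mainly help precision.

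**Conclusion.** The length-of-stay test is inconsistent with the design and with the SAP's own statement on dependence. With the NEST ICC range and equal caseloads, a nominal 5% test runs at about 5% to 9% with 4 families per clinician. If discipline explains half of the clustering, the size at ICC 0.1 is roughly 6% to 9% across the layouts.

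A reader might infer that these tests run at 13%. The documents do not support that as a general figure: it needs 240 families, only 30 clinicians, an ICC at the top of a range stated for another outcome, and no discipline effect. Nor is it a strict ceiling, since unequal caseloads could push that corner to about 15%. A reader might also infer a threat to the main result. There is none, because NEST is analysed with a hierarchical model that has a physician random effect. Confidence is high that the defect exists and low on its size. Severity is moderate to minor.

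**What to change.** Replace the Wilcoxon test with a rank test that treats the clinician as the cluster. There are two options, which are not interchangeable, so the SAP should name one:

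- a clustered rank-sum test with clinician as cluster; or
- the Wilcoxon statistic with a p-value from re-randomising clinicians within the strata actually used.

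The second option first needs the strata settled. Design & Procedures lists gender, clinical experience and discipline, whereas the Aim 2 model describes its race, service-time and ICU-type terms as the stratification variables. These must be reconciled.

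Suggested wording: *Hospital and ICU length of stay are compared between arms with a rank-sum test that accounts for clustering by randomised clinician.*

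The SAP is written in the past tense, so any length-of-stay p-values already produced should be recomputed. The cost is one sentence and a few lines of code, with no new data; the protocol already lists R. The downside is that the p-values become somewhat larger.

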Assuming that a participant receives a NEST score of \geq 15, regardless of clinician randomization, the participant will continue with the following study procedures:

- Survey 2 (T2) to be completed within 3 days (0/+1 day) of T1 completion.
- Survey 3 (T3) to be completed within 7 days (0/+3 days) of T1 completion
- Survey 4 (T4) to be completed within 3 months (90 days, 0/+3 days) of T1 completion.

Should a participant receive a NEST score of \geq 15 and be randomized to an intervention clinician, the participant will be contacted by the intervention clinician have a family meeting. Family meetings are to occur after the completion of T1 but prior to the completion of T2. Given the short timeframe between T1 and T2, the clinician can conduct the family meeting in a variety of settings: in the ICU at bedside, in a private conference room and/or location within the waiting room (at the choice of the participant), and/or over the phone.

In conjunction with Aims 2 and 3 of the RCT, the study team will simultaneously enroll patient/family dyads into the ancillary study. The ancillary study will include a total of 250 enrolled patient/family dyads. Eligible participants will be approached for consent at the time of the ICU admission. Participants enrolled into the ancillary study will be those participants whose current attending clinician is not enrolled in the RCT and/or their identified primary race and ethnicity is something other than White or African American /Black and Non-Hispanic. Participants enrolled in the ancillary study, like the RCT, must meet study eligibility criteria.

Participants enrolled into the ancillary study will complete an ICUconnect profile and then be asked to complete the following surveys:

- Survey 1 (T1) to be completed within 24 hours of consent.
- Survey 2 (T2) to be completed within 3 days (0/+1 day) of T1 completion.
- Survey 3 (T3) to be completed within 7 days (0/+3 days) of T1 completion
- Survey 4 (T4) to be completed within 3 months (90 days, 0/+3 days) of T1 completion.

Given that the targeted patient population involves individuals who are seriously ill and/or injured, the study team expects that there is a high likelihood that death could occur while the patient/family dyad's participation is ongoing. Should a patient pass away while study participation is ongoing, the following will occur:

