- If the patient passes after the completion of T1 but prior to the completion of T2, the patient/family dyad will be withdrawn from the study.
- If the patient passes after the completion of T1 and T2 but prior to T3 completion, the patient /family dyad will remain eligible to continue study participation; however, the study team will be mindful and sensitive regarding approach and may skip T3. It is not considered a deviation if the family completes T3 prior to the study team enabling the "skip" option within ICUconnect.

• If the patient passes after the completion of T1, T2, and T3 but prior to completion of T4, the study team may wait 1 month before asking the family to complete the fourth and final study survey. It is not considered a deviation if the family completes T4 1 month late.

In regards to survey completion, it is understood, given the nature of the study design (self-directed participant survey completion), that surveys may not be completed in the specified protocol windows. The study team will provide participant education at the time of consent regarding the importance of completing surveys in a timely manner. In addition, the study team will follow-up with participants (patient /family dyads and clinicians) via phone, email, and in-person to complete study surveys and/or family meetings, as applicable.

The study consists of the following statuses for patient/family dyads:

- Consented: an individual(s) who meets all eligibility criteria and has voluntarily agreed to participate in the study (RCT or ancillary).
- Enrolled: an individual whom, after consent is obtained, completes the first survey.
 - Nte: if a participant is enrolled in the RCT study and receives a NEST score of < 15, he/she
 is deemed a screen failure and is therefore no longer enrolled. If a participant is enrolled in
 the ancillary study, he/she does not need to meet a NEST threshold for enrollment.
- Screen Fail: any participant who is enrolled into the RCT and receives a score of < 15.
- Withdrawn by PI: any participant who does not comply with study specific requirements (i.e. such as timely completion of study surveys, specifically T1 and/or T2) or is found to be by the principal investigator no longer appropriate for this study due to current state of being (physical, mental and /or emotional).
- Withdrawn by Self: voluntary withdraw of participant from study for any reason.
- Completed: any participant (RCT or ancillary) who completes 75% of study visits.

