- -Study (R21 vs. ICUconnect intervention arm)
- -Gender
- -Trigger (present vs. absent)
- -Race
- -Age
- -Medical vs Surgical ICU (place of eligibility and recruitment)
- -NEST at T1 and T2 (responder vs. non-responder)
- -Technology confidence
- -Status (completed)

Families who meet the criteria listed above will be contacted via telephone and/or email and asked to participate in this portion of the project using the approved telephone and/or email consent template. Each individual will be asked to read, review, and sign/date an eConsent attesting to their willingness to participate.

As part of this aim, families who choose to participate will be asked to complete a 15 minute audio recorded interview in which the family member will be asked a series of questions pertaining to their loved one's hospitalization and ICU admission, the status of their loved one (alive or deceased), and then their overall experience related to their loved one's care in the ICU and their interactions with the clinical care team.

Selection of Subjects

• List inclusion/exclusion criteria and how subjects will be identified.

To identify eligible patient/family dyads for consent in both the RCT and the ancillary study, the study team will utilize the electronic medical record (EMR) known as EPIC for screening purposes. The study team will complete a daily review of the EMR, specifically reviewing each ICU unit and associated beds for patients who meet study criteria.

For both the RCT and the ancillary study, eligible participants are those patients who are at least at moderate risk of death or disability. In addition, while patients will not be excluded based on diagnosis, it is anticipated that most patients will predominantly be diagnosed with cardiorespiratory failure, stroke, trauma, and/or septic shock.

Eligible clinicians will be identified by the Principal and sub investigators. Clinicians must meet the criterion listed below. In addition, the selected clinician for consent and subsequent randomization should be scheduled to be on service at least 8 weeks per year (or the equivalent in terms of 12-hour shifts).

Inclusion Criteria (Patients, Pre-Consent)

- 1. ≥18 years of age
- 2. Patients must be on mechanical ventilation in a study ICU for ≥ 24 hours
 - a. For those patients whose mechanical ventilation is interrupted for <72 hours, they will remain eligible for study participation.

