 - b. If a patient is intubated on the day of eligibility but then subsequently extubated the same day, the patient remains eligible for the study as long as consent and T1 are completed within 8 hours of extubation.
- 3. Death must not be imminent (< 24 hours)

Inclusion Criteria (Family Members, Pre-Consent)

- 1. One family member per patient is eligible.
- 2. The family member must be \geq 18 years old.
- 3. The family member must be self-described as the individual (related or unrelated) who provides the most support and with whom the patient has a significant relationship.

Inclusion Criteria (Clinician, Pre-Consent)

1. Patients' bedside ICU attending physicians on the day of family consent are eligible.

Exclusion Criteria (Patients, Pre-Consent)

- 1. Patients who are admitted to an ICU at the index hospital >14 days will be ineligible for participation.
- 2. Patients who are on comfort care or are planned to undergo withdrawal of treatment within the following 48 hours of enrollment will be excluded.
- Prisoners
- 4. Patients who have no known family or surrogate.
- 5. Patients who are transferred to a non-study ICU or non-study clinician will be excluded if they are enrolled into the RCT only.

Exclusion Criteria (Family Members, Pre-Consent)

- 1. Family members will be excluded if they lack English fluency or have other limiting factors that inhibit their ability to use the app (e.g. literacy, blindness, etc).
- 2. Family members will be excluded if they are not directly involved in decision making, are unreachable or unavailable.
- 3. Family members will be excluded if they are <18 years of age.
- 4. Family members will be excluded if they are unable to consent (e.g., dementia, cognitive impairment).
- 5. Prisoners.
- 6. For the RCT only: family members who self-identify as Hispanic and/or self-identify most with a racial group other than White or Black will be excluded.
 - a. Ethnic and racial exclusions do not apply to the ancillary study.

Exclusion Criteria (Patient/Family Dyad Post-Consent)

- 1. Patient dies before T2 is completed.
- 2. Family members will be excluded from the RCT, but not the ancillary study, who have a very low need burden (NEST < 15) after the completion of T1.
- 3. For the primary RCT, participants are also excluded if the randomized physician leaves ICU service or is replaced by a non-participating ICU physician < 2 calendar days after family completes T1.

For Aim 4 RCT (or Aim 3 Ancillary Study) Only:

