Aim 3 Analyses: A hierarchical linear model will again be the primary modeling strategy for the Aim 3 analyses. For this Aim, however, the model will include patient-race interaction terms and will have the following form: Yijk= b0+ b1(Blacki) + b2(T2) + b3(T2*Blacki) + b4(T2*intk) + b5(T2*Blacki*intk) + b6 (racek)+ b7(servicetimek) + b8(ICUtypek)+ bik+ ck+ eijk, where Yijkis the NEST score for family iat time jand physician k. In this model, Blackiis the indicator variable for whether a patient is Black (value of 1) or White (value of 0). Racial disparities in unmet needs at baseline are represented by the estimated value of b1. That is, the estimated baseline mean for White families is b0 and the estimated baseline mean for Black families is b0 + b1, so if the estimate of b1is positive, this indicates that prior to the intervention, Black patients have more unmet needs than White patients. Post-treatment, the Black-white mean difference among usual care group families is BWuc = (b0 + b1 + b2 + b3) - (b0 + b2), and among intervention group families is BWint = (b0 + b1 + b2 + b3 + b4 + b5) - (b0 + b2 + b4). Hypothesis 3a will be tested by the difference between BWint and BWuc, indicating that racial disparities unmet needs are reduced in the intervention group as compared to the control group. The estimated difference, p-value, and 95% confidence intervals will be calculated via estimate statements in PROC MIXED. Additionally, estimated values and confidence intervals will be calculated for BWint as compared to b1 to quantify the magnitude of reduction from baseline. A similar hierarchical linear model will be used to examine the reduction in racial disparities of quality of patient-centered care and test Hypothesis 3b.

Missing Data: The survey data may contain missing values in any of the clinician-level and patient-level variables due to drop-out, death, or item non-response. Our primary analysis technique, hierarchical models, allow for unbalanced or incomplete data and will be fit with maximum-likelihood methods to preserve the missing at random assumption. Additionally, we will thoroughly explore reasons for dropout, and depending upon the type and scope of missing data, variables may be multiply imputed as recommended by guidelines.46Note that if needed, we will utilize imputation methods that account for the multiple levels of correlation inherent in the clustered data structure.

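### The Wilcoxon test on hospital and ICU length of stay has no rule for patients who die in hospital, so a difference between arms cannot be interpreted on its own

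*SAP*

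**What the plan says.** The last sentence of the SAP states that "treatment group differences in hospital and ICU length of stay were examined with a Wilcoxon test". That is all either document says on analysing length of stay; the protocol's Data Analysis & Statistical Considerations section does not mention it. The Missing Data paragraph there names death only as a source of missing survey values ("due to drop-out, death, or item non-response"), which does not tell the analyst what to do with a stay that ends in death.

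Deaths are expected. Under Selection of Subjects, "eligible participants are those patients who are at least at moderate risk of death or disability". Under Design & Procedures the team expects that "there is a high likelihood that death could occur while the patient/family dyad's participation is ongoing".

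The handling of a dyad depends on when the patient dies:

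- **Between T1 and T2:** "the patient/family dyad will be withdrawn from the study" (Design & Procedures). The post-consent exclusion list under Selection of Subjects agrees: "Patient dies before T2 is completed". T2 falls about three days after T1: "Survey 2 (T2) to be completed within 3 days (0/+1 day) of T1 completion".
- **After T2:** the dyad stays in. The rule that begins "If the patient passes after the completion of T1 and T2 but prior to T3 completion" keeps it eligible, and so does the rule for deaths between T3 and T4.

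The adverse event text in Design & Procedures adds that patient deaths will not be documented or reported by the study, so no safety table would show them by arm.

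**The concern.** A hospital or ICU stay ends in one of two ways, discharge alive or death, and the two mean opposite things for the patient. A rank test on the raw number of days cannot tell them apart. If one arm has more deaths, or the same number of deaths sooner, its stays look shorter even when every survivor stays exactly as long as a survivor in the other arm.

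The setting makes this more than a formality. Patients have been ventilated for at least 24 hours. The intervention centres on a family meeting with the ICU attending, and goal-concordant care is one of the SAP's outcomes. An effect on when death occurs is not claimed anywhere, but it cannot be ruled out, and chance imbalance in deaths would act in the same way. Without deaths by arm in the same table, a reader who sees a shorter stay cannot tell faster recovery from earlier death.

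**Working it through.** There is no length-of-stay figure in the documents to reproduce: no effect size, power, mortality rate or time to death. The check is therefore of the mechanism, under stated assumptions.

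**Inputs from the documents.** Two-sided 0.05 level (so 2.5% in each direction); 80 per arm (160 families in the power paragraph) or 120 per arm (240 dyads in Design & Procedures); deaths before T2 removed, with T2 about 3 days after T1.

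**Assumptions.** Survivor stay lognormal with median 14 days in both arms; time to death lognormal with median 5 to 14 days; log-SD 0.7 for both; mortality 20-50%; stay ends at death; deaths before day 3 removed to mimic the T2 rule; clustering ignored. The documents do not say from which day a stay is counted, so one clock is used for stay, death and the day-3 cut.

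**Step 1: hand check without the T2 exclusion.** Take 35% mortality in both arms and median time to death 8 days (control) versus 5 days (intervention). The Wilcoxon test responds to P, the chance that a random intervention stay is shorter than a random control stay. The difference of two log stays has SD 0.7 × √2 = 0.990.

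| Pair (intervention, control) | Weight | P(intervention shorter) | Product |
|---|---|---|---|
| survivor, survivor | 0.65² = 0.4225 | 0.5 | 0.2113 |
| death, survivor | 0.35 × 0.65 = 0.2275 | Φ((ln 14 − ln 5)/0.990) = 0.8508 | 0.1936 |
| survivor, death | 0.65 × 0.35 = 0.2275 | Φ((ln 8 − ln 14)/0.990) = 0.2859 | 0.0650 |
| death, death | 0.35² = 0.1225 | Φ((ln 8 − ln 5)/0.990) = 0.6825 | 0.0836 |

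P = 0.5535 instead of 0.5, although survivors are identical. With n per arm the standard error under no difference is √((2n + 1)/(12n²)).

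- n = 80: SE 0.0458, z = 0.0535/0.0458 = 1.17, and 1 − Φ(1.96 − 1.17) = 21%.
- n = 120: SE 0.0373, z = 1.43, and 1 − Φ(1.96 − 1.43) = 30%.

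Simulation of the same case gives 22% and 32%.

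**Step 2: simulation with deaths before day 3 removed** (2,000 trials per scenario, Monte Carlo error at most √(0.5 × 0.5/2000) = 1.1 points). Entries are the share of trials with a significantly shorter intervention stay; nominal 2.5%.

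| Deaths, control vs intervention | Median days to death | 80 per arm | 120 per arm |
|---|---|---|---|
| 35% vs 35% | 8 vs 8 | 2.5% | 2.6% |
| 20% vs 20% | 8 vs 5 | 5% | not available |
| 35% vs 35% | 8 vs 5 | 8% | 12% |
| 50% vs 50% | 8 vs 5 | 17% | 25% |
| 50% vs 50% | 10 vs 5 | 42% | 58% |
| 25% vs 40% | 6 vs 6 | 14% | 16% |
| 30% vs 50% | 6 vs 6 | 18% | 28% |
| 25% vs 40% | 14 vs 14 | 2.6% | 1.9% |

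The last row shows the boundary: when deaths come as late as discharges, the effect disappears.

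**Step 3: what the T2 exclusion does.** At 35% mortality and 8 versus 5 days it cuts the rate from 22% to 8% (80 per arm) and from 32% to 12% (120 per arm). But it does not act equally on the arms. The share removed is 0.35 × Φ((ln 3 − ln 8)/0.7) = 0.35 × 0.081 = 2.8% in control and 0.35 × Φ((ln 3 − ln 5)/0.7) = 0.35 × 0.233 = 8.1% in intervention. Of 80 per arm that is about 2 versus 6 or 7 patients.

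**Step 4: a death-aware analysis.** With death given the worst rank, the scenarios with more deaths at median 6 days no longer favour intervention. The 25% versus 40% case is flagged against intervention in 32% (80 per arm) or 45% (120 per arm) of trials, and the 30% versus 50% case in 55% or 72%. In the timing-only scenarios at 35-50% mortality some 7-12% rejections remain, because the T2 exclusion leaves unequal numbers of deaths.

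**The case against.** Five points can be made in the plan's defence.

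1. *The SAP does not say that deaths count as short stays.* A reader might infer that it does. It is silent, and a survivors-only Wilcoxon, or length of stay shown beside mortality, would also fit the sentence. This stands. The defect is the missing rule: the possible readings can give different answers, and a survivors-only test would itself condition on a post-randomization outcome.

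2. *The earliest deaths are already removed.* Imminent death, comfort care and planned withdrawal of treatment exclude patients before consent, and death before T2 removes them afterwards. This stands in part. The T2 rule often halves the effect or better in the timing scenarios, but does not eliminate it. It also operates after clinicians are randomized, over the interval in which the family meeting takes place. Nor is it stated that the rule defines the length-of-stay analysis set; if it does not, the larger figures apply.

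3. *The size rests on assumptions.* This stands. The expectation of death covers participation up to 90 days, whereas only in-hospital deaths cut a hospital stay short. With gamma-distributed stays, 40% mortality, mean time to death 14 versus 10 days and 80 per arm, 14-19% of two-sided tests were significant without the exclusion and 10-13% after removing deaths before day 4 (nominal 5%). With a day-3 cut and a survivor mean of 20 days, the rate was 7% at 20% mortality and 5% at 10%.

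4. *No conclusion depends on this test.* This stands. The objectives and hypotheses do not mention length of stay, no passage calls a shorter stay a benefit, and the main conclusions are tied to the pre-specified hypotheses on unmet needs and quality of care.

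5. *Worst rank is a contestable choice here.* This stands. In a palliative care trial that also measures goal-concordant care, treating every death as the worst outcome is debatable, so it belongs only in a sensitivity analysis.

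**Conclusion.** The point holds in a limited form. The SAP plans a plain Wilcoxon test on hospital and ICU length of stay and gives no rule for in-hospital deaths, in a trial that expects deaths and keeps dyads after T2 when they occur. On the natural default, where the stay ends at death, a difference in the number or timing of deaths can produce a difference in length of stay with no change among survivors.

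The size cannot be fixed from the documents. For a timing shift of 8 versus 5 days at 35-50% mortality in both arms, with pre-T2 deaths removed, it is 8-25% against a nominal 2.5%. It is about 5% at 20% mortality with 80 per arm, and there is none when deaths are as late as discharges. All of these figures assume identical survivor stay and ignore clustering.

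Two stronger readings should be resisted. One is that the intervention changes when patients die; the protocol states no such hypothesis, and none is needed for the point. The other is that the trial would report a false benefit; the documents neither define a shorter stay as beneficial nor rest a main conclusion on it. Length of stay is not the primary outcome, so this is a desirable improvement and not a threat to the trial's main result.

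**What to change.** - State how a stay ending in death is counted, and whether dyads removed for death before T2 are in the length-of-stay analysis set.
- Report the number of in-hospital deaths by arm in the same table as hospital and ICU length of stay, including deaths between T1 and T2.
- Describe length of stay by arm separately for survivors and decedents. Keep this descriptive, since vital status arises after randomization.
- Add one death-aware sensitivity analysis, for example time to discharge alive with death as a competing event, or a rank test with death as the worst rank.
- Use a method for the comparison that accounts for physician clusters, for example a clustered rank-sum test or a permutation of clinician assignments. Randomization is by clinician, and the SAP itself says that outcomes sharing a physician are not independent, but the plain Wilcoxon test treats them as if they were.

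The cost is a few table rows and one short analysis. The only extra variable is vital status at discharge, which should be obtainable: the team must know of deaths to apply its survey rules, and it already collects data from the medical record. The statement that patient deaths are not documented sits in the adverse event text and need not prevent this. The SAP is written in the past tense, so if the analysis has already been run, the additions can be made in the report and labelled as such.
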